Appendix C Table 8: Management of neutropenia, leukopenia and and thrombocytopenia

Toxicity	Study treatment dose adjustment
CTCAE Grade 1-2	Investigator judgement to continue treatment or if dose interruption, this should be for a maximum of 4 weeks; appropriate supportive treatment and causality investigation
CTCAE Grade 3-4	Dose interruption until recovered to CTCAE grade 1 or better for a maximum of 4 weeks. If repeat CTCAE grade 3-4 occurrence, dose reduce olaparib to 250 mg BID as a first step and 200 mg BID as a second step

8.4.2.3 Management of prolonged haematological toxicities while on study treatment.

If a patient develops prolonged haematological toxicity such as:

- ≥ 2 week interruption/delay in study treatment due to CTC grade 3 or worse anaemia and/or development of blood transfusion dependence
- ≥ 2 week interruption/delay in study treatment due to CTC grade 3 or worse neutropenia ($ANC < 1 \times 10^9/L$)
- ≥ 2 week interruption/delay in study treatment due to CTC grade 3 or worse thrombocytopenia ($Platelets < 50 \times 10^9/L$) and/or development of platelet transfusion dependence

Check weekly differential blood counts including reticulocytes and peripheral blood smear. If any blood parameters remain clinically abnormal after 4 weeks of dose interruption, the patient should be referred to haematologist for further investigations. Bone marrow analysis and/or blood cytogenetic analysis should be considered at this stage according to standard haematological practice. Study treatment should be discontinued if blood counts do not recover to CTC Grade 1 or better within 4 weeks of dose interruption.

Development of a confirmed myelodysplastic syndrome/acute myeloid leukemia or other clonal blood disorder should be reported as an SAE and full reports must be provided by the investigator to AstraZeneca Patient Safety. Olaparib treatment should be discontinued if patient's diagnosis of MDS and/or AML is confirmed.

Further details are provided in the Investigators Brochure.

8.4.2.4 Management of non-haematological toxicity for ceralasertib and olaparib

Acute toxicities in the all treatment arms should be managed as medically indicated, with temporary suspension of IP and initiation of supportive care as clinically indicated by the treating physician. Treatment must be interrupted if any NCI-CTCAE Grade 3 or 4 non hematologic AE occurs which the Investigator considers to be related to the administration of the study treatment(s). Treatment should not be restarted until the toxicity has resolved to Grade \leq 1.

Repeat dose interruptions are permitted, for a maximum of 28 days. Any patient who develops a Grade 3 or 4 non-haematologic toxicity that does not resolve to \leq Grade 1 within this period, should be removed from the study treatment. Once a dose is reduced, re escalation is not permitted.

A summary of the dose reduction guidance for ceralasertib and olaparib is presented earlier.

At the first occurrence of CTCAE grade 3 and 4 non-haematological toxicity, ceralasertib and olaparib should be held until resolution of toxicity. At the resolution of the first occurrence of any of these toxicities, no change must be made to dose. At the second occurrence, upon resolution of toxicity, ceralasertib and/or olaparib should be reduced by the 1st dose reduction for non-haematological toxicity to 120 mg qd for 7 days and/or olaparib 250 mg BID q 12 hours daily ([Appendix C Table 5](#) and [Appendix C Table 9](#)) Despite this change, at the third occurrence, upon resolution of toxicity, ceralasertib and/or olaparib should be reduced by the 2nd dose reduction to 120 mg qd for 4 days and 200 mg bid q 12 hours daily ([Appendix C Table 5](#) and [Appendix C Table 9](#)). If despite these changes, there is a fourth occurrence of toxicity, the patient should permanently discontinue study drug. Please note that, for each dose reduction, the investigator may choose to reduce ceralasertib or olaparib or both drugs. If only one drug is dose reduced, the second drug may be reduced as an additional step. Refer to [Appendix C Table 9](#) for specific dose modification guidance regarding non-haematological toxicity.

Appendix C Table 9: Summary of guidance on the management of non-haematologic toxicity for ceralasertib and olaparib

Toxicity	Ceralasertib and olaparib
Any non-haematologic toxicity (CTCAE grade ≥ 3)	
1st occurrence
 
Withhold dose and monitor at least weekly for up to 28 days until recovery to \leqCTCAE grade 1 then resume at original dose level. If a clinical CTCAE give supportive measures and rule out other causes; if a laboratory AE is not resolving within two weeks contact Sponsor for guidance
 
If symptoms do not recover to \leqCTCAE grade 1, contact Sponsor and consider discontinue ceralasertib and olaparib .

	
2nd occurrence
 
Withhold dose for up to 28 days until recovery to \leqCTCAE grade 1 then resume at 1st reduced dose level for non-haematological toxicity (see Appendix C, table 4). The investigator may choose to reduce ceralasertib or olaparib or both drugs. If only one drug is dose reduced, the second drug may be reduced as an additional step if the toxicity recurs.
 
If symptoms do not recover to \leqCTCAE grade 1, contact Sponsor and consider discontinue ceralasertib and olaparib.

	
3rd occurrence
 
Withhold dose for up to 28 days until recovery to \leqCTCAE grade 1 then resume at 2nd reduced dose level for non-haematological toxicity (see Appendix C, table 4). The investigator may choose to reduce ceralasertib or olaparib or both drugs. If only one drug is dose reduced, the second drug may be reduced as an additional step if the toxicity recurs.
 
If symptoms do not recover to \leqCTCAE grade 1, contact Sponsor and consider discontinue ceralasertib and olaparib.

Toxicity	Ceralasertib and olaparib
	4th occurrence
	Off-study drug

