Appendix B Table 9 Non-hematologic toxicity dose modification and management

Electrocardiogram QT corrected interval prolonged		
QTc Value	CBDP	AZD1775
QTc 450-480 ms (males) or 470-480 (females)	No dose modifications	Hold. Once QTc interval has returned to pretreatment status and correction of possible electrolyte imbalance has been made, resume at next lower dose level.
QTc 481-500 ms	No dose modifications	Hold. Seek cardiologist advice.

QTc \geq 501 ms	Discontinue treatment	Discontinue treatment
Shift from baseline of \geq 60ms	Discontinue treatment	Discontinue treatment
<hr/>		
CTCAE version 4.03	CBDP	AZD1775
Grade 0 - 2	No dose modification	No dose modification
Grade 3 ^{b,c,d}	Hold ^a	Hold ^a
Grade 4 ^b	Hold until toxicity resolves to Grade \leq 1. Resume with 1 dose level reduction	Hold until toxicity resolves to Grade \leq 1. Resume with 1 dose level reduction
Second repeat incidence of Grade 3 or 4 toxicity (except nausea, vomiting, fatigue, malaise, lethargy, anorexia, alopecia)	Discontinue treatment	Discontinue treatment
<hr/>		
Hepatic		
<hr/>		
CTCAE v4.03	CBDP	AZD1775
Grade 1-2	No dose modification	No dose modification
Grade 3 or 4 (manifested as elevations in ALT, AST, ALP, or bilirubin)	Hold until resolves to Grade \leq 1 or baseline, then resume CBDP with a 1 level dose reduction. If not resolved within 28 days, discontinue CBDP.	Hold until resolves to Grade \leq 1 or baseline, then resume study drug with a 1 level dose reduction. If not resolved within 28 days, discontinue study drug.
<hr/>		
Diarrhea or mucositis		
<hr/>		
CTCAE v4.03	CBDP	AZD1775
Grade 1-2	No dose modification	No dose modification
Grade 3 or 4 (or requiring hospitalization)	Hold ^a	Hold ^a
<hr/>		
Nephrotoxicity		
<hr/>		
CTCAE v4.03	CBDP	AZD1775
Grade 0-1	No dose modification	No dose modification

Grade ≥ 2 Hold until resolves to Grade ≤ 1 or Hold^a
baseline, then resume CBDP with
a 1 level dose reduction. If not
resolved within 28 days,
discontinue CBDP.

Neurotoxicity		
CTCAE v4.03	CBDP	AZD1775
Grade 1	No dose modification	No dose modification
Grade 2	Hold until toxicity resolves to Grade ≤ 1 . Resume with 1 dose level reduction.	No dose modification
Grade 3 or 4	Discontinue treatment	Discontinue treatment

- ^a Hold until toxicity resolves to \leq Grade 1 and then resume at the same dose with no modification.
- ^b Dose reduction for nausea and vomiting should be made only if Grade 3 or Grade 4 toxicity occurs in spite of maximum anti-emetics.

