- Absolute neutrophil count (ANC) $\geq 1.5 \times 10^9 / L$ without the use of G-CSF
 - Platelet count $\geq 100 \times 10^9/L$ with no platelet transfusion in the past 28 days
 - Total bilirubin ≤ 1.5 x institutional upper limit or normal (ULN) unless the patient has documented Gilbert's Syndrome
 - Aspartate aminotransferase (AST) / alanine aminotransferase (ALT) ≤ 2.5 x institutional ULN unless liver metastases are present in which case they must be ≤ 5 x ULN

- Patients must have a creatinine clearance (CrCl) estimated using the Cockcroft-Gault equation of ≥ 51 mL/min:

$$\text{Estimated CrCl} = \frac{(140 - \text{age}[\text{years}]) \times \text{weight} (\text{kg}) \times (F)^a}{\text{serum creatinine} (\text{mg/dL}) \times 72}$$

^a where $F=0.85$ for females and $F=1$ for males

11. Evidence of post-menopausal status or negative urinary or serum pregnancy test for female pre-menopausal patients. Women will be considered post-menopausal if they have been amenorrheic for 12 months without an alternative medical cause. The following age-specific requirements apply:
 - Women <50 years of age would be considered post-menopausal if they have been amenorrheic for 12 months or more following cessation of exogenous hormonal treatments and if they have luteinizing hormone and follicle-stimulating hormone levels in the post-menopausal range for the institution or underwent surgical sterilization (bilateral oophorectomy or hysterectomy).
 - Women ≥ 50 years of age would be considered post-menopausal if they have been amenorrheic for 12 months or more following cessation of all exogenous hormonal treatments, had radiation-induced oophorectomy with last menses >1 year ago, had chemotherapy-induced menopause with >1 year interval since last menses, or underwent surgical sterilization (bilateral oophorectomy or hysterectomy).
12. Women of childbearing potential and their partners, who are sexually active, must agree to the use of 2 highly effective forms of contraception in combination from the signing of the informed consent, through the period of taking study treatment and for at least 1 month after last dose of study drug (s), or they must totally / truly abstain from any form of sexual intercourse (as described in Appendix G).

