8.4 Dose modifications and management of investigational product related toxicities

Guidelines for the management of hematological and non-hematological AEs for ceralasertib and olaparib are described below. Given the aggressive nature of relapsed or refractory SCLC and the lack of an effective standard of care in this clinical setting, doses of ceralasertib and olaparib will be modified by cycle (see Section 2.1 of the CSP). Subsequent cycles will be further adjusted to patient tolerance and investigator judgement.

Toxicity will be assessed utilizing the NCI Common Terminology Criteria for Adverse Event (CTCAE) version 4.03 unless otherwise specified. Every effort should be made to administer trial treatment at the planned dose and schedule. However, patients experiencing toxicities related to the trial treatment may have their dose modified as outlined in this section.

Any toxicity observed during the course of the study could be managed by interruption of study treatment or dose reductions, and initiation of supportive care as deemed appropriate by the investigator. In the event that a patient has not recovered sufficiently to enable the next chemotherapy cycle to start, then the cycle should be delayed until the toxicity has recovered sufficiently to allow further dosage. The maximum cycle delay is permitted in 28 days. Repeat dose interruptions are allowed as required, for a maximum of 28 days on each occasion. Any patient requiring a toxicity related dose delay of more than 28 days from the intended day of the next scheduled dose must be discontinued from the study unless there is approval from the Study Physician for the patient to continue.

If Day 1 treatment with either ceralasertib or olaparib is interrupted, then both study medications will be delayed until the combination can be resumed. Dose adjustments will be based on the organ system exhibiting the greatest degree of toxicity.

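### Arm C gives three different consequences for a Grade 3–4 non-haematological toxicity unresolved at 28 days, and its Grade 1 restart level takes no account of the grade at entry

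*Protocol*

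**What the plan says.** Three places in Appendix C cover a non-haematological toxicity that has not settled after 28 days.

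- **Section 8.4.2.4, text.** The time limit is "Repeat dose interruptions are permitted, for a maximum of 28 days". On resuming, it says "Treatment should not be restarted until the toxicity has resolved to Grade" 1 or lower. A patient with a Grade 3 or 4 event that has not reached "Grade 1 within this period, should be removed from the study treatment".
- **Section 8.4.2.4, Table 9**, to which the text sends the reader for specific guidance. At the first occurrence: "Withhold dose and monitor at least weekly for up to 28 days until recovery to" Grade 1 or lower. The second and third occurrences carry the same 28-day hold. If recovery fails at any of the three, the instruction is "contact Sponsor and consider discontinue ceralasertib and olaparib".
- **Section 8.4, general rule.** A patient whose toxicity-related delay exceeds 28 days from the next scheduled dose "must be discontinued from the study unless there is approval from the Study Physician for the patient to continue".

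The Arm C entry criteria bear on the recovery level. Exclusion 29 exempts Grade 2 peripheral neuropathy from the bar on persisting toxicity, and exclusion 14 leaves neuropathy of Grade 2 or above to case-by-case discussion. Inclusion criterion 10 sets the AST/ALT limit at 2.5 x "institutional ULN unless liver metastases are present in which case they must be" no more than 5 x ULN.

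**The concern.** A stopping rule should give one answer for one set of facts. Here a site following the text takes the patient off treatment, a site following the table may keep the patient on hold while it talks to the Sponsor, and a site following the parent section discontinues the patient from the study unless a waiver is granted. The parent section also differs from the text in what is being stopped. The master protocol treats leaving treatment and leaving the study differently: section 4.9 expects visits and data collection to continue after treatment stops, while section 4.10.2 ends study observation other than survival follow-up.

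The second worry is the recovery level. A fixed Grade 1 target is attainable by returning to baseline only if baseline was Grade 1 or better, and Arm C does not require that of everyone it admits.

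At stake is the meaning of discontinuation for toxicity in a small single-arm cohort spread over about 30 sites. Section 2.2.1 of the master protocol makes Review Committee decisions depend on the totality of the data and the benefit-risk assessment, and this count feeds into that.

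**Working it through.** The protocol gives no figure to reproduce on this point. The check is a comparison of its statements, with a little arithmetic for size.

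**Step 1: the three rules side by side.**

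| Place (Appendix C) | Time limit | Consequence | Exception | What stops |
|---|---|---|---|---|
| 8.4.2.4 text | 28 days of interruption | removal | none stated | study treatment |
| 8.4.2.4 Table 9, 1st–3rd occurrence | hold of up to 28 days | Sponsor contact; stopping considered | not needed, as nothing is mandatory | both drugs |
| 8.4 general rule | delay over 28 days from the next scheduled dose | mandatory discontinuation | Study Physician approval | the study |

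**Step 2: do they apply to the same patient?** Take a first treatment-related Grade 3 event, with dosing held and the event still at Grade 2 on day 30. The text and the table are both met. The general rule counts from the next scheduled dose. Olaparib is taken twice daily throughout the cycle, so that clock starts within about a day of the hold and has also run out. The outcomes are then off treatment (text), on hold pending a Sponsor discussion (table), or out of the study unless approved (general rule). They agree only at a fourth occurrence, where text and table both end study drug.

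**Step 3: the restart level against the entry criteria.** Let e be the grade at entry. Restart requires Grade 1 or lower, so full return to baseline satisfies it only if e is at most 1.

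- *Neuropathy.* Exclusions 14 and 29 can admit e = 2. A patient who worsens to a treatment-related Grade 3 and returns to Grade 2 is back at baseline, yet 2 > 1, so restart is not allowed. Under the 8.4.2.4 text this patient is removed at 28 days. No outside figure is needed.
- *AST/ALT with liver metastases.* Entry is allowed up to 5 x ULN. The protocol names CTCAE v4.03 but does not print its AST/ALT limits, so let the Grade 1 ceiling be g x ULN (an assumption). Patients entering above g and up to 5 x ULN start above the restart level:

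| Assumed g | Entry values above the restart level |
|---|---|
| 2.5 | >2.5 to 5 x ULN |
| 3 | >3 to 5 x ULN |
| 4 | >4 to 5 x ULN |
| 5 or more | none |

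This part therefore holds for any g below 5 and fails otherwise. Without liver metastases the entry limit is 2.5 x ULN, and the problem arises only if g is below 2.5.

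**Step 4: size.** Appendix C section 3 plans up to 20 patients, and master section 9.5.7 places the interim at 10. One patient classified differently changes the discontinuation rate by 1/20 = 5 percentage points, or 1/10 = 10 at the interim. How many patients would be affected cannot be derived from the protocol.

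**The case against.** The best defence reads the three statements as a hierarchy. Section 8.4 sets the default and its waiver, the 8.4.2.4 text repeats the default, and Table 9 describes the contact through which a waiver would be sought. The text itself defers to Table 9 and uses advisory wording for removal. Part of this stands: section 8.4 softens the conflict. It does not remove it, because the text contains no waiver, the table contains no mandatory stop, and neither cites section 8.4 for the exception. The difference between leaving treatment and leaving the study is also untouched.

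On liver enzymes the defence is stronger. A reader might infer that patients with liver metastases are bound to be stopped for values they had at entry. The documents do not show this. The Grade 1 limit is not printed. The 8.4.2.4 text makes interruption mandatory only for events the Investigator considers treatment-related, so a rise attributed to progressing metastases is not clearly caught there. Table 9 also sends a laboratory event not resolving within two weeks to the Sponsor at first occurrence.

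A reader might also infer that Arm C is wrong because Arm B's hepatic row (Appendix B Table 9) allows recovery to Grade 1 "or baseline, then resume study drug with a 1 level dose reduction". Master section 2.4 declares the arms independent, the drugs differ, and Arm B's own general Grade 4 row has no baseline alternative. The contrast shows that the authors knew of the device. It is not an error in itself.

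Finally, the analysis is descriptive, reasons for stopping are recorded, and RECIST assessments count whether or not treatment has stopped (master section 9.4.1.1). To call toxicity discontinuation in Arm C uninterpretable would go too far.

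**Conclusion.** The point holds as an internal inconsistency. Arm C states three consequences for one event, differing in whether stopping is mandatory, whether it can be waived, and whether it means leaving treatment or the study. This rests on the protocol's wording alone.

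The gap in the recovery level also holds on the protocol alone for Grade 2 peripheral neuropathy. For AST/ALT it is conditional on a CTCAE Grade 1 ceiling below 5 x ULN, and no percentage rise or fall should be quoted for it.

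The consequence is a toxicity-discontinuation count that is inconsistently defined, at 5 percentage points per patient in a full arm of 20. It does not invalidate the response analysis. It should be corrected because it governs what sites do with individual patients.

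**What to change.** 1. Reconcile section 8.4, the 8.4.2.4 text and Table 9 of Appendix C so that one consequence is stated for a Grade 3–4 non-haematological toxicity unresolved at 28 days. State whether a waiver exists and who grants it, from what day the 28 days run, and whether the patient leaves study treatment or the study.
2. Reconcile the recovery level with inclusion criterion 10 and exclusions 14 and 29 by stating how recovery is judged when the entry grade is already above Grade 1.
3. In the same edit, correct Table 9's cross-reference for the reduced dose levels. It cites Table 4, which lists laboratory tests, whereas the dose levels are in Table 5.

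Which clinical rule applies is for the sponsor to decide, and this review proposes none. The cost is a few sentences in a protocol amendment. No extra data, visits or patients are needed.

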8.4.1 Dose Reduction: Ceralasertib + Olaparib Combination

For ceralasertib, study treatment can be dose reduced according to the following dose modification table. A maximum of 2 dose reduction steps are permitted. If after the second dose reduction treatment is not tolerated, no further dose reduction is allowed, and study treatment should be discontinued. Dose re-escalation is not permitted. Further dose modifications are described in Appendix C Table 5 below.

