Appendix C Table 5 : Cohort C Guidance for dose reductions for ceralasertib and olaparib*

Dose Level	Ceralasertib	Olaparib
Initial dose level	160 mg QD Days 1-7	300 mg BID Days 1-28
1 st dose reduction	Dose reduce either AZD6738 or Olaparib or Both	
Haematological Toxicity	160mg QD Days 1-4	250 mg BID Days 1-28
Non-Haematological Toxicity	120mg QD Days 1-7	250 mg BID Days 1-28
2nd dose reduction	Dose reduce either Ceralasertib or Olaparib or Both	
	120 mg QDQ Days 1-4	200 mg BID Days 1-28
3 rd dose reduction: No further reduction permitted, withdraw patient and treat as clinically indicated. Dose must not be re-escalated even if toxicities have resolved in subsequent cycles.		

* Ceralasertib and olaparib may be reduced stepwise within each dose reduction level e.g., dose reduce olaparib first followed by ceralasertib if the AE recurs. Dose reductions for anaemia should occur for olaparib first (with consideration to a simultaneous dose reduction in ceralasertib depending on the severity, duration and recurrence of the anaemia). If a dose reduction is required for neutropenia, leukopenia and thrombocytopenia, olaparib and ceralasertib should be dose reduced simultaneously as there is a greater frequency associated with ceralasertib. For a second dose-reduction, follow the guidance above on which of either, or both agents, to dose-reduce depending on the observed toxicity.

Appendix C Table 8 provides guidance for hematologic toxicity (neutropenia, leukopenia and thrombocytopenia) observed any time during the study treatment period. **For Day 1 of each cycle please check the required blood counts to commence treatment in Appendix C Table 6.**

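### In Arm C the non-haematological dose rule takes no account of an earlier cytopenia reduction, so if ceralasertib is the drug chosen at the second Grade 3-4 event, the named dose raises its cycle total from 640 to 840 mg

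*Protocol*

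**What the plan says.** Appendix C Table 5 starts ceralasertib at 160 mg on Days 1-7 and olaparib at 300 mg BID. It splits the first ceralasertib reduction by toxicity type: "160mg QD Days 1-4" for haematological toxicity, and 120 mg on Days 1-7 for non-haematological toxicity. Olaparib goes to 250 mg BID in both cases. The second reduction is one row shared by both types: ceralasertib 120 mg on Days 1-4, olaparib 200 mg BID. At a third reduction the table says "No further reduction permitted, withdraw patient and treat as clinically indicated", and it adds "Dose must not be re-escalated even if toxicities have resolved in subsequent cycles".

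The footnote to Table 5 covers cytopenias other than anaemia: "If a dose reduction is required for neutropenia, leukopenia and thrombocytopenia, olaparib and ceralasertib should be dose reduced simultaneously". Table 8, which covers the same cytopenias, names only olaparib for reduction.

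Section 8.4.1 sets the limit: "A maximum of 2 dose reduction steps are permitted". It does not divide that limit by toxicity type.

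Section 8.4.2.4 and Table 9 work from a different count, the number of Grade 3-4 non-haematological occurrences. At the first, 8.4.2.4 leaves the dose unchanged. At the second, ceralasertib and/or olaparib is cut; ceralasertib "should be reduced by the 1st dose reduction for non-haematological toxicity to 120 mg qd for 7 days", olaparib to 250 mg BID. At the third, the doses are 120 mg for 4 days and 200 mg BID. At the fourth, treatment stops. The investigator may reduce either drug or both. The same section states "Once a dose is reduced, re escalation is not permitted".

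**The concern.** The counter in 8.4.2.4 and Table 9 starts from zero for non-haematological events, whatever reduction the patient has already had. Table 5 and 8.4.1 describe a single ladder of two steps. The two schemes agree for a patient who has only had non-haematological toxicity. They part for a patient who was first reduced for neutropenia, leukopenia or thrombocytopenia and then has two Grade 3-4 non-haematological events.

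For that patient the dose written in 8.4.2.4 lies sideways from the current one: less drug per day, on more days, with a larger total. One site may follow the sentence in 8.4.2.4 and another the ladder in Table 5, and each can say it followed the protocol. What is at stake is dosing after repeated severe toxicity, and consistency between sites. No endpoint, sample size or analysis depends on it.

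**Working it through.** The plan gives no cycle totals, so there is no figure of its own to reproduce. The inputs are the Table 5 doses and the 28-day cycle.

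**Ceralasertib per cycle = daily dose x dosing days**

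- Initial: 160 x 7 = 1120 mg
- First reduction, haematological: 160 x 4 = 640 mg
- First reduction, non-haematological: 120 x 7 = 840 mg
- Second reduction, shared: 120 x 4 = 480 mg

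**Patient already at the haematological first level** (160 mg Days 1-4, olaparib 250 mg BID), at the second Grade 3-4 non-haematological event:

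- As 8.4.2.4 is worded, with ceralasertib chosen: 640 to 840 mg. Ratio 840/640 = 1.3125, so +31%. Daily dose 120/160 = 0.75, so -25%. Dosing days 4 to 7.
- As 8.4.2.4 is worded, with olaparib chosen: 250 mg BID to 250 mg BID, no change.
- By the Table 5 ladder: 640 to 480 mg. Ratio 480/640 = 0.75, so -25% with dosing days unchanged at 4. Olaparib goes to 200 mg BID (400 against 500 mg per day, -20%).

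**How much of the earlier cut is returned.** The haematological step removed 1120 - 640 = 480 mg per cycle. The move to 840 mg gives back 840 - 640 = 200 mg, and 200/480 = 42%.

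**Number of reductions.** One haematological step, plus the steps at the second and third non-haematological occurrences, makes 1 + 2 = 3, against a cap of 2 in 8.4.1.

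**Sensitivity to how the cytopenia was handled.** If the site followed Table 8 and cut only olaparib, ceralasertib is still at 160 mg Days 1-7. The move to 120 mg Days 1-7 is then a true reduction: 1120 to 840 mg, 840/1120 = 0.75, so -25%. The rise therefore appears only where ceralasertib was cut as well, which is what the Table 5 footnote calls for.

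**The case against.** The strongest reply is that the protocol already answers the question. Table 5 splits only the first step by toxicity type and shares the second. The cap in 8.4.1 is not split. The re-escalation ban stands in 8.4.2.4 itself, ahead of the dosing sentence, and that section cites Table 5. Read together, a first-level patient goes next to 120 mg Days 1-4. Section 8.4 also leaves later cycles to the investigator's judgement of tolerance. This shows which dose is sensible. It does not remove the conflict: 8.4.2.4 and Table 9 name another dose, and nothing says that a haematological step counts towards their levels. Because the daily dose falls, a site could fairly hold that it has not re-escalated.

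Two limits do stand. The move happens only if the investigator chooses to reduce ceralasertib, and only if ceralasertib was cut for the cytopenia.

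A reader might infer more, and the documents do not support it:

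- *That a second-level patient has no stop rule in 8.4.2.4.* The section cites Table 5, which holds that rule.
- *That returning to seven dosing days is shown to impair platelet recovery.* Appendix C 2.4.5 refers to 21 drug-free days, and dosing on Days 1-7 leaves 28 - 7 = 21.
- *That Table 9 contradicts itself after a one-drug reduction.* Its second row lets the other drug be cut on recurrence, while its third row gives the second reduced level. The Table 5 footnote allows stepwise reduction within a level and the wording is permissive, so this is largely intended flexibility.

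**Conclusion.** The point holds as an inconsistency between dosing rules. For a patient at ceralasertib 160 mg Days 1-4 and olaparib 250 mg BID, the second Grade 3-4 non-haematological event leads, on the wording of 8.4.2.4 and Table 9, to 31% more ceralasertib per cycle over three more days, or to no change in olaparib. The Table 5 ladder would give 25% less ceralasertib, or 20% less olaparib.

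This assumes that the cytopenia was handled by the Table 5 footnote rather than by Table 8 alone, and that cycle total and dosing days matter as well as daily dose. Table 5 supports the latter, since its haematological step works by cutting days.

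Severity is minor. The sequence needs a cytopenia reduction followed by two Grade 3-4 non-haematological events, the document gives no frequency for it, and Appendix C section 3 plans for up to 20 patients. No statistical figure changes.

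**What to change.** State in 8.4.2.4 and Table 9 that:

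- reduction levels are counted per drug across all toxicity types;
- a toxicity reduction may not raise the daily dose or the number of dosing days of either drug, leaving untouched the olaparib re-escalation that 9.7.1 allows after washout of a CYP3A inhibitor;
- from either first-level ceralasertib dose (160 mg Days 1-4 or 120 mg Days 1-7) the next level is 120 mg Days 1-4, and from olaparib 250 mg BID it is 200 mg BID.

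Two optional tidy-ups can go in at the same time: say which row of Table 9 governs the third occurrence when only one drug was cut at the second, and correct the reference in Table 9 from Table 4 (the laboratory list) to Table 5.

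The cost is a few sentences and a letter to sites. No extra patients, visits or procedures are needed.
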